3 STUDY ENDPOINTS

- Primary 1: Subjective questionnaires of product evaluation (Duke Sensory Scale, Product Evaluation Scale, Drug Effects, Hedonic Attribute), withdrawal (MNWS, QSU-B, PANAS), and readiness to quit (contemplation ladder).
- Primary 2: Number of cigarettes smoked per week during the field period.
- Secondary: Awareness and beliefs about filter ventilation and perceptions of messaging.
- Secondary: Exhaled CO is defined as level of CO measured in exhaled breath after a 15 s breathhold. This is typically 10ppm or above in daily smokers and <3 ppm in nonsmokers.
- Secondary: Smoking topography as assessed by particulate matter retained on used filters.

Roswell Park Protocol Number: I 757820

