5 STUDY TIMELINES

5.1 Duration of an Individual Subject's Participation in the Study

The proposed study consists of multiple videoconferencing sessions (a total of 3) throughout a 2-week field study. Following informed consent, participants will be randomly assigned to 1 of 4 message conditions and use the assigned product for 2 weeks. This 2-week field study involves participants logging their use of tobacco products, while the weekly videoconferencing sessions involve additional questionnaires and guidance about field data collection.

Roswell Park Protocol Number: I 757820

	Data Collection Sessions (Weekly)			Field (Daily for 14 days)
	Video 1	Video 2	Video 3	Ecological Momentary Assessment
Tobacco Use Behavior				
Cigarettes per Day	X	X	X	X
Other Tobacco Use	X	X	X	X
Context of Use (e.g., location)				X
Questionnaires				
Message Perceptions (response, health risk, purchase)	X All messages	X Randomly Assigned Message	X Randomly Assigned Message	
Vent Awareness	X	X	X	
Product Evaluation (Duke Sensory, Product Evaluation Scale, Drug Effects, Hedonic Attribute)	X	X	X	X Select Items
Readiness to Quit (Contemplation Ladder)	X	X	X	
Withdrawal (MNWS, QSU-B, PANAS)				X Select Items
Attention to Messaging				X
Biomarkers				
Exhaled CO				X
Topography via Filter Analysis				X

Estimated date for the investigators to complete this study

Data collection should be completed by 12/31/2022.

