5 TRIAL DELAY DISCOUNTING

You will now complete a series of decision-making tasks. You will be asked to make choices between different amounts of money given to you now or after a delay. These are hypothetical choices, but please choose your answer as if the items were to be delivered as described. Each task will start with some brief instructions on the screen. Read these instructions and press the 5 key on the keyboard when you are ready to begin. There are no right or wrong answers in the tasks, just choose which option you prefer in each case. Please take your time and answer thoughtfully. To select the option on the left side of the screen, press the left arrow, and to select the option on the right side of the screen, press the right arrow.

[Task implemented on computer via REDCap]

IN SESSION MEASURES (Administered after each cigarette)

Product Evaluation Scale

Think about your general experience when using the product you just tried.

Please answer the following questions about the product using the scale below [7-point scale, Not at all – Extremely]

Cigarette Product Code: _____	
1. Was it satisfying?	_____
2. Did it taste good?	_____
3. Did it make you dizzy?	_____
4. Did it calm you down?	_____
5. Did it help you concentrate?	_____
6. Did it make you feel more awake?	_____
7. Did it reduce your hunger for food?	_____
8. Did it make you nauseated?	_____
9. Did it make you feel less irritable?	_____
10. Did you enjoy the sensations in your mouth?	_____
11. Did it immediately reduce your craving for a cigarette?	_____
12. Did it relieve withdrawal symptoms?	_____
13. Did it relieve the urge to smoke?	_____
14. Was it enough nicotine?	_____
15. Was it too much nicotine?	_____
16. Was it easy to use?	_____

Roswell Park Protocol Number: I 757820

17. Were there bothersome side effects? _____

18. Would you be comfortable using the product in public? _____

19. Did you still have a craving for a cigarette after using the product? _____

20. Are you concerned you would become dependent on the product? _____

21. Did you enjoy using the product? _____

22. Would you be willing to use the product long term? _____

JUSTER PURCHASE INTENTION

How likely are you to purchase the product you just tried in the next month?

- 10 = Certain, practically certain
- 9 = Almost sure
- 8 = Very probable
- 7 = Probable
- 6 = Good possibility
- 5 = Fairly good possibility
- 4 = Fair possibility
- 3 = Some possibility
- 2 = Slight possibility

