- 1 = Very slight possibility
- 0 = No chance, almost no chance

Duke Cigarette Sensory Evaluation | 1-7 Not at all – Extremely|

[figure not shown]
Please rate the puffs you just took. Circle the number that best answers each question.

1. How much did you like the puffs you just took?
2. How satisfying were the puffs you just took?
3. How high in nicotine do you think the puffs were?
4. How similar to your own brand were the puffs?

Using the same scale as above, rate how strong the puffs were in the following places.

Roswell Park Protocol Number: I 757820

5. Strength of puffs on tongue?
6. Strength of puffs in nose?
7. Strength of puffs in back of mouth & throat?
8. Strength of puffs in windpipe?
9. Strength of puffs in chest?

[figure not shown]

Roswell Park Protocol Number: I 757820

DRUG EFFECTS / LIKING SCALE

Place a vertical line at the point on the scale that indicates how you feel about each of the statements right now.

1. Do you feel any study product effects?
2. Do you feel any good study product effects?
3. Do you feel any bad study product effects?
4. How much do you like the study product?
5. How much do you desire the study product?
6. How much would you like to use this product again?

Roswell Park Protocol Number: I 757820

HEDONIC ATTRIBUTE PROFILE

Draw	1 TOO EASY	2	3	4 JUST RIGHT	5	6	7 TOO HARD
Mouthful of Smoke	1	2	3	4	5	6	7
	TOO LITTLE			JUST RIGHT			TOO MUCH
Impact	1 TOO LITTLE	2	3	4 JUST RIGHT	5	6	7 TOO MUCH
Irritation	1 TOO LITTLE	2	3	4 JUST RIGHT	5	6	7 TOO MUCH
Strength	1 TOO MILD	2	3	4 JUST RIGHT	5	6	7 TOO STRONG
Smoothness	1 TOO SMOOTH	2	3	4 JUST RIGHT	5	6	7 TOO HARSH
Tobacco Taste	1 TOO LITTLE	2	3	4 JUST RIGHT	5	6	7 TOO MUCH
Tobacco Taste	1 UNPLEASANT	2	3	4 NEUTRAL	5	6	7 PLEASANT
Overall Taste	1 UNPLEASANT	2	3	4 NEUTRAL	5	6	7 PLEASANT
Aftertaste	1 UNPLEASANT	2	3	4 NEUTRAL	5	6	7 PLEASANT
Similarity to Usual brand	1 VERY DIFFERENT	2	3	4	5	6	7 VERY SIMILAR

Roswell Park Protocol Number: I 757820

PANAS (10 item) [1-5 Not at all – Extremely]

The next part involves a number of words that describe different feelings and emotions. I'll say each word, and you can indicate to what extent you feel this way RIGHT NOW, on a scale from 1-5. 1 means you don't feel this way at all or slightly feel this way right now. 2 means feeling this way a little, 3 means moderately, 4 means quite a bit, and 5 means extremely feeling this way right now.

1. Inspired
2. Afraid
3. Alert
4. Upset
5. Excited
6. Nervous
7. Enthusiastic
8. Scared

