This message:
Discourages me wanting to smoke
Makes smoking seem unpleasant to me
Makes me concerned about health effects of smoking

Negative Affect

How much did the label make you feel:
Anxious
Sad
Scared
Guilty
Disgusted

Roswell Park Protocol Number: I 757820

Thinking of Harms

How much did the labels make you think about:
The chemicals in the smoke of the cigarettes
Health problems caused by smoking
The harm your smoking might be doing to you
The harm your smoking might be doing to other people

Would you support or oppose a policy that required this label to appear on cigarette packages?
Strongly oppose – Strongly support

Would you support or oppose a policy that required this label to appear in advertising for cigarettes?
Strongly oppose – Strongly support

Remote Data Collection – EMA Schedule and Questionnaires

3 Daily Reports – 11 am, 4pm, 9pm (assessments < 5min)

How many cigarettes have you smoked since the last prompt?

How many of these cigarettes were research cigarettes?

How many of these cigarettes were not research cigarettes?

How you used any other tobacco products since the last prompt?

If yes: What product? How many times did you use it?

Please record your product weight with the provided scale.

RIGHT NOW: How would you rate your (0 – 100 VAS):

- Craving
- Irritability
- Anxiousness/nervousness
- Difficulty Concentrating
- Stress
- Bored
- Calm/Relaxed
- Happy
- Alert
- Enthusiastic

Provide Reminder to collect all cigarette butts in provided materials, store used pods

11 am Only (additional questions)

Hedonic Attribute Profile: In the past day, how would you rate the research cigarettes (1-7 Likert)

Draw

Irritation

Smoothness

Roswell Park Protocol Number: I 757820

Strength

Tobacco Taste

Similarity to Usual Brand

Product Evaluation Scale (1 - 7 Likert):

Was it satisfying?

Did it taste good?

Did it calm you down?

Did you enjoy the sensations in your mouth?

Did it reduce your craving for a cigarette?

Were there bothersome side effects?

Did you enjoy using the product?

Would you be willing to use the product long term?

Record CO measurement

9pm Only (additional questions):

Record CO measurement

Reflect on today as a whole: How would you rate your (0 – 100 VAS)

- Craving
- Irritability
- Anxiousness/nervousness
- Difficulty Concentrating
- Stress
- Bored
- Calm/Relaxed
- Happy
- Alert
- Enthusiastic

Thinking of the cigarettes you smoked today: How would you rate (0 – 100 VAS)

- Tastes like my own brand

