Please keep track of the amount of cigarettes and other tobacco you use. The scheduled prompts will ask you to report the number of cigarettes you've smoked. The random prompts will ask you to report on the situation in which you last used your product, such as the location and if smoking was allowed. We also ask that you store all used cigarette butts in the provided materials

Here are examples of the questions you will be asked at each assessment (show questionnaires). Do you have any questions?

We are also providing you with a CO monitor that will connect with your phone to take a CO measurement each night (demonstrate use).

We are also providing you with a scale to weigh other tobacco products that you may use, such as an e-cigarette or smokeless tobacco. If you use these other products, we would like you to weigh your product (e.g., pod, tank, dip tin) at the beginning and end of each day. If you are close to finishing your product and may start a new one, please weigh both the older and newer one at the beginning and end of the day.

Two additional times during the field study, we will ask you to videoconference with us as a study check-in and to have you respond to some questionnaires.

These are the cigarettes we are asking you to use during the field study (provide research cigarettes). Please use only these cigarettes and do not tamper with the cigarette pack. At random points in the study, we may ask you to take a picture of the cigarette pack.

Do you understand the procedures for the field study? Please call us if you have any questions.

Videoconferencing Sessions 2 & 3

Hello, today we are going to have you fill out a questionnaire. I will send it to you now. Have you been regularly storing your cigarette butts. Can I see how you are storing them?

Compliance: Your compliance has been great. Thank you!

Or: Your compliance has not met the standards. Please respond to more prompts or you may be discontinued for the study. Do you have any questions about the study procedures that may help you respond to more prompts?

Session 3 only:

Please pack up your supplies to prepare a return shipment. Can I see how you've stored your supplies in the box?

When we receive your materials, we will send you payment for completing the study. Thank you for participating.

Roswell Park Protocol Number: I 757820

Ads for the website/mobile app:

RESEARCH PARTICIPANTS NEEDED

Searching for:
21-69 year old daily cigarette smokers

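### Three Primary 1 scales are worded for use straight after a cigarette, but no video-session procedure includes smoking, so the session ratings have no defined, timed index cigarette

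*Combined protocol and SAP*

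**What the plan says.** Section 3 defines Primary 1 as "Subjective questionnaires of product evaluation (Duke Sensory Scale, Product Evaluation Scale, Drug Effects, Hedonic Attribute), withdrawal (MNWS, QSU-B, PANAS" together with readiness to quit. The section 5.1 schedule has a single row, "Product Evaluation (Duke Sensory, Product Evaluation Scale, Drug Effects, Hedonic Attribute", marked at Videos 1, 2 and 3, with selected items in the field.

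Appendix C prints these forms after the heading "IN SESSION MEASURES (Administered after each cigarette". Their instructions are:

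- Product Evaluation Scale: "Think about your general experience when using the product you just tried", with a line for a cigarette product code.
- Duke: "Please rate the puffs you just took".
- Drug Effects/Liking: a mark that "indicates how you feel about each of the statements right now". Five of its six items name the study product.
- Hedonic Attribute Profile: no timing instruction is printed.

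The sessions are home videoconferences (section 6.1.2) of half an hour (section 11.3). Section 11.3 describes questionnaires, training and, at Session 3, packing of materials. The Appendix D script for Sessions 2 and 3 opens "Hello, today we are going to have you fill out a questionnaire. I will send it to you now" and goes on to butt storage and compliance.

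Section 22.1 analyses change in product responses by linear regression on message, sex and other tobacco use, with no rule about time since smoking.

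**The concern.** A rating of current drug effect, or of puffs just taken, depends on how long ago the person smoked and what they smoked. In a laboratory session both are fixed by design. In a questionnaire-only videoconference neither is, unless the form supplies a reference.

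As printed, a participant at Session 2 or 3 must choose which cigarette to rate. It may be minutes or hours old. It may also be a non-research cigarette, since the EMA form counts these separately. Different participants will answer different questions on a primary endpoint.

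Drug Effects has a further problem at Video 1: it asks about study-product effects before the field period starts. Any change score from that visit compares two different things.

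**Working it through.** No figure in the plan is at issue, so the check is mainly a comparison of sections.

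**1. Do the procedures contain a cigarette to rate?**

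- Section 11.3: no smoking step in Session 1, 2 or 3.
- Appendix D: no instruction to smoke in any session.
- Section 5.1: exhaled CO and filter analysis are marked only in the field column.
- Pointing the other way: the Appendix C heading, and section 11.1, which speaks of filters from the sessions.

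Appendix D also mentions a laboratory session. The CO-boost definition in section 22 needs CO before and after smoking, which the schedule does not provide. Carried-over laboratory text would explain both, but the documents do not settle it. What is established is an unreconciled conflict.

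**2. How many items rest on the session form alone?** Counting items printed in Appendix C:

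| Scale | Session items | Items in EMA forms | Session only |
|---|---|---|---|
| Duke | 9 | 4 | 5 |
| Product Evaluation | 22 | 8 | 14 |
| Drug Effects | 6 | 0 | 6 |
| Total | 37 | 12 | 25 |

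The five session-only Duke items are the five on strength of puffs by location.

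**3. Are the EMA versions anchored?** Partly.

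- Hedonic: "In the past day, how would you rate the research cigarettes".
- Duke: the most recent cigarette, not restricted to research cigarettes.
- Product Evaluation: no anchor of its own.

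**4. How far could time since the last cigarette vary?** Assume 16 waking hours and even spacing; neither is in the plan. The gap is 16/CPD hours, where CPD is cigarettes per day, and the mean time since the last cigarette at a random moment is half the gap.

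- Eligibility minimum, 5/day: gap 16/5 = 3.2 h, mean 1.6 h.
- Rate implied by section 22.1 (25% equals 3.9 CPD): 3.9/0.25 = 15.6/day; gap 16/15.6 = 1.03 h, mean 0.51 h.
- 20/day: gap 16/20 = 0.8 h, mean 0.4 h.

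These figures illustrate the spread between participants. They do not estimate an effect on any score.

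**5. What does the variation do to a contrast between arms?** Write the score as Y = μ(arm) + e + u, where u is the part due to uncontrolled timing and product. If randomised arms have the same distribution of u, it cancels from the difference in means. If u is independent of e, the standard error is multiplied by √(1 + Var(u)/Var(e)). Precision falls, but the mean contrast is not attenuated. It is shifted only if the mean of u differs by arm, through smoking timing or use of non-study cigarettes. The documents give no value for Var(u).

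**6. Drug Effects at baseline.** Section 5.1 marks it at Video 1. Section 11.3 lists only Duke, Product Evaluation and Hedonic for the usual-brand baseline. Session 1 precedes field use, so the study-product items have no referent there.

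**The case against.** The strongest reply is that the ratings are anchored well enough in practice. By Sessions 2 and 3 participants have had the assigned cigarettes for about one and two weeks, and the script tells them to use only these. Five of the six Drug Effects items name the study product, and items 4 to 6 (liking, desire, use again) are not purely acute. The Product Evaluation Scale asks for general experience, which can be answered after a week of use. Much of this stands: the clear mismatch is Duke and the first three Drug Effects items, with Product Evaluation affected less.

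A second reply is that EMA covers the gap. It does so for Hedonic and for some Duke and Product Evaluation items, and adds evening ratings of taste, satisfaction, enjoyment and craving relief. It does not reach the 25 items counted above. A reader might also infer that suitable past-day wording already exists in EMA for every scale; it is printed only for Hedonic.

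A third reply is that recency can be recovered from the diary. Section 11.3 does ask participants to record each smoking event. The printed forms, however, count cigarettes since the previous prompt. Scheduled prompts are 2.5 hours apart in section 11.4, and the counting reports 5 hours apart in Appendix C. That is coarse against a typical gap of about 1 hour.

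Finally, the plan hypothesises no effect of messages on smoking behaviour, and nothing in the documents shows one on smoking timing. The route to bias is therefore conditional.

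**Conclusion.** The point holds in a limited form. The session forms of Duke, Drug Effects and, less so, Product Evaluation presuppose a cigarette that no session procedure supplies. These Primary 1 ratings therefore have no defined, timed index cigarette. The expected consequence is added variance of unknown size and scores of unclear meaning; bias would require message condition to alter smoking timing or use of non-study cigarettes. For Drug Effects, change from Video 1 is not interpretable.

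Three stronger readings are tempting and not supported:

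- That no cigarette is smoked in any session. This is inferred from silence, and the Appendix C heading and section 11.1 point the other way.
- That the ratings are unconnected to study-product exposure. Participants are supplied with the product and told to use only it; what is missing is a defined and timed exposure.
- That noise pulls the message contrasts toward zero. Noise in a continuous outcome that is unrelated to arm widens the interval and leaves the mean difference unchanged.

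The item counts rest on the forms as printed. The timing figures rest on the assumed 16 hours and even spacing. Primary 1 as a whole is not undermined, but the defect affects a primary measure and is cheap to remove.

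**What to change.** Reconcile the section 5.1 schedule, sections 11.1 and 11.3, the Appendix C session forms and the Appendix D script. If smoking in session was intended, the procedures must say so. If not:

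- Give each session form a stated reference: the usual brand at Session 1 and research cigarettes at Sessions 2 and 3. Use the most recent research cigarette for Duke and Drug Effects, and a stated recall period for Product Evaluation.
- Remove Drug Effects from Video 1 and analyse it as a post-baseline score.
- Add one item at Sessions 2 and 3: minutes since the last cigarette, and whether it was a research cigarette. Use it descriptively or in a sensitivity analysis. Because it is measured after randomisation, it should not enter the main model.

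The cost is revised REDCap wording and one short item. The small downside is that the wording departs from the laboratory forms, as the EMA versions of Duke and Hedonic already do.

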11.2 Treatment

This study will use two types of cigarettes. One set of cigarettes are commercially available Marlboro cigarettes (Philip Morris USA, Richmond, VA), all combustible King size (83mm) cigarettes consisting of filler, filter paper, tipping paper, cigarette paper, tipping glue and seam glue. Specific varieties are listed in the table. Products will be sourced at retail from local outlets.

Alternatively, participants may receive investigational “roll your own” (RYO) cigarettes that will be prepared in the laboratory. These cigarettes will be made to match the commercially available Marlboro cigarettes. These cigarettes will be prepared with conventional tobacco (e.g., Good Stuff) rolled using an automatic rolling machine (e.g., Powermatic III+) and packaged into 20 rod packs. The investigational RYO cigarettes will use ventilated filter tubes (e.g., ~25-37% filter ventilation). The dose of nicotine in these RYO cigarettes will be similar to conventional cigarettes.

Within each pair of products is a nonmenthol and menthol equivalent. Participants who report regularly smoking menthol cigarettes will receive the menthol versions for the study.

Variety	Vent %	Filter length (mm)	Tobacco weight (mg)
Special Blend Smooth Mellow	30.6	27	625.1
Smooth Fresh Menthol	37.6	27	630.8

Additionally, cigarettes will be paired with messaging about filter ventilation. This message will be affixed to the front exterior of each package provided to participants.

- No Message (e.g., unaltered cigarette pack).
- Neutral Message: “Nothing about this product’s color or name means that it will protect a smoker from the health risks of smoking.”
- Compensation Message: “This product has a ventilated filter. Filter vents increase how deeply a smoker inhales without them knowing, which can increase the health risks of smoking.”
- Blocking Message: “This product has a ventilated filter. Be sure not to block the vent holes with your fingers or lips, which can increase the health risks of smoking.”

Roswell Park Protocol Number: I 757820

With these conditions, ‘no message’ serves as a true control (smoking as normal), while the neutral message serves as a control message to determine if added messaging impacts behavior/perceptions, even if that message is not informational. The compensation and blocking messages will determine if added messaging about the health risks of filter ventilation affect behavior/perceptions, and which type of message has the greater impact.

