In the event of REDCap being inaccessible for a study visit, .pdf files or paper copies of the consent will be provided to the participants and the participants will be able to sign and return or submit a photo of the signed copy.

The participant will then be randomized to 1 of 4 message conditions (No message, Neutral message, Compensation message, Blocking message) and arrangements will be made to mail, deliver, or have participants pick up study materials (study cigarettes with pack messages, CO

Roswell Park Protocol Number: I 757820

monitor, scales, butt collection materials, shipping materials, etc.). Participants will be provided with two weeks of materials.

Session 1. Session 1 will occur upon receipt of study materials by the participant. Participants will complete a baseline intake questionnaire including smoking and tobacco use history, nicotine dependence scales, SCQ, TRIRISK, delay discounting, respiratory symptoms, and knowledge, attitudes, and beliefs about filter vents. In addition, participants complete questionnaires on message perceptions (response to messaging, health risk, purchase intention) for all pack messages. Questionnaires also will be used to get baseline assessments of the user's usual brand of cigarettes (Duke Sensory Scale, Product Evaluation Scale, Hedonic Attribute Scale). Participants will be instructed to record each smoking event using the EMA app provided (described in more detail below) and to retain all spent cigarette butts and unused product. Participants will be informed that they are free to use other tobacco products (though they will not be provided as part of the study), and that these should be recorded using EMA. Participants will be provided for cigarettes for a total of two weeks, with the amount determined by normal self-reported weekly consumption rounded to nearest whole pack.

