11.4 Data To Be Collected

- **Baseline measures and covariates will assess:**
 - Demographics (age, sex, race/ethnicity, education, income)

Roswell Park Protocol Number: I 757820

- Tobacco use behaviors (consumption, brand, menthol preference, past quit attempts)
- Delay discounting
- A series of previously used items will assess knowledge and perceptions of filter vents.^{113,117}
- Nicotine dependence will be assessed using:
 - Fagerström Test for Nicotine Dependence (FTND¹¹⁸)
 - PROMIS

Behavioral aspects of cigarette dependence will be assessed using:

- The Glover-Nilsson scale^{120,121}
- The different scales are used to capture different dimensions of tobacco dependence.¹²²
- Exhaled air CO will be collected by the participants twice each day using a personal CO monitor provided by the researchers. The CO monitors provided are coVita iCo™ Smokerlyzers®, which are intended for research and consumer use and are compatible with a Smartphone or tablet (iOS or Android).

Perceptions of product messaging: In this study, we are interested in risk perceptions, smoking-related expectancies, and behavioral intentions. We will assess risk perceptions for specific products using a risk ladder.¹²⁹ More generalized perceptions of risk for cancer are captured using the tripartite risk (TRIRISK) measure, which captures deliberative, affective, and experiential components of risk perception.¹³⁰ The adult smoking consequences questionnaire (SCQ) will assess smoking-related expectancies.^{103,131} Behavioral intention is assessed using Juster's consumer purchase probability scale, a widely used marketing metric.¹³²⁻¹³⁴ Additional questions will include responses to messaging (e.g., message was powerful, memorable).

Responses to product use will be assessed in a number of ways: Response to nicotine dose will be assessed using the Minnesota Nicotine Withdrawal Scale (symptoms of nicotine withdrawal).¹³⁵ Cigarette craving in field will be assessed using the Brief QSU commonly used in cue reactivity research. Behavioral economic measures will assess product demand. A delay discounting task will assess preference for immediate reward,¹⁴⁸ while purchase tasks will be used to estimate level and elasticity of demand.¹⁴⁹⁻¹⁵¹ Sensory measures will be collected using the Duke Sensory Scale and Hedonic Attribute Scale. Drug effect measures include the Product Evaluation Scale and Drug Effects/Liking Scale.

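### The only printed purchase-intention item asks about a product just tried and names no message, so it cannot supply the per-message ratings due at Session 1, and what it refers to at Sessions 2 and 3 is unclear

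*Combined protocol and SAP*

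**What the plan says.** Purchase intention is planned as a perception of the message. The schedule in Section 5.1 has a row beginning "Message Perceptions (response, health risk, purchase", marked for all messages at Video 1 and for the randomly assigned message at Videos 2 and 3. Section 11.3 says of Session 1 that "participants complete questionnaires on message perceptions (response to messaging, health risk, purchase intention) for all pack messages". For Session 2 it limits message perceptions to the participant's own condition, and Session 3 repeats the Session 2 questionnaires. In Section 11.4, under the paragraph on perceptions of product messaging, "Behavioral intention is assessed using Juster's consumer purchase probability scale".

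Appendix C prints one Juster item: "How likely are you to purchase the product you just tried in the next month", answered from 0 to 10. It falls in the block headed "IN SESSION MEASURES (Administered after each cigarette").

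On timing, Section 11.3 states that "Session 1 will occur upon receipt of study materials by the participant". On the product, Section 11.2 gives two commercial Marlboro varieties (nonmenthol and menthol) bought at retail. It also allows an investigational laboratory-made alternative: "These cigarettes will be prepared with conventional tobacco (e.g., Good Stuff) rolled using an automatic rolling machine".

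**The concern.** The instrument and its planned use do not match. The plan wants a rating attached to a message. The printed item asks for a rating attached to a cigarette that has just been smoked, and its heading suggests that it was written for a session in which cigarettes are smoked one after another. This study has no such session.

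Two things are at stake. First, the Session 1 comparison of all messages within the same person, on purchase intention, cannot be made from the printed item. Second, the Session 2 and 3 answers have no matching Session 1 value, so change in purchase intention under the assigned message cannot be computed. The premise in Section 1.1 is that messages reduce the appeal of smoking. Purchase intention is the measure that Section 11.4 chooses for the behavioural side of message response.

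**Working it through.** This is a check of documents against each other. The plan gives no figure for this measure to reproduce.

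**1. Has anything been tried by Session 1?** Section 11.3 places Session 1 at receipt of materials. Its content is the intake questionnaire, message perceptions, baseline product ratings of the usual brand, and training. No smoking is scheduled. The Appendix D script runs in the same order: baseline questionnaires, including those on messages, come first, and the research cigarettes are introduced afterwards.

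**2. Could the item be read another way at Session 1?**
- If the product is taken to be the usual brand, the question is identical for every message, because none is mentioned.
- If a participant opened a study pack early, that pack carries only the assigned condition, so the other three conditions still have no object.

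Neither reading produces one rating per message.

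**3. Does another item fill the gap?**
- Cigarette Purchase Task (Appendix C): fixes the usual brand, varies price and mentions no message.
- Message questionnaires (Appendix C: responses to pack messaging, message and effect perceptions, negative affect, thinking of harms, policy support): no purchase question.
- Product Evaluation Scale: asks about willingness to use the product long term, with no message and no purchase.

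No printed item asks about purchase by message.

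**4. How many ratings are affected?** Section 22.1 expects 300 participants at Visit 1. If all four conditions are rated, 300 × 4 = 1,200 ratings. If only the three printed messages are rated, 300 × 3 = 900.

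**5. What does the item give at Sessions 2 and 3?** Participants have by then used the assigned product for about one or two weeks. Section 11.3 randomizes them to four conditions, and Section 11.2 puts the message on the front of each pack supplied. A difference between arms in the mean answer therefore estimates a message effect on intention to buy the study product, although the wording omits the message. Two ambiguities remain:
- no cigarette is smoked in these video sessions, so a question about something just tried fits poorly;
- for the laboratory-made cigarette the documents describe no way to buy it.

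**6. Is the Session 2 and 3 signal lost?** Let f be the share of each arm given the laboratory-made cigarette, which the documents do not state. Take as an extreme assumption that all of them answer 0 in every arm. A true difference D among the rest then becomes (1 − f) × D:
- f = 0: (1 − 0) × D = D
- f = 0.5: (1 − 0.5) × D = 0.5D
- f = 1: (1 − 1) × D = 0

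Even under that assumption the comparison is empty only if everyone receives the laboratory version.

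**The case against.** The strongest reply is that randomization does the work. At Sessions 2 and 3 the arms differ by pack message, so the item need not name the message for the between-arm comparison to be valid, and naming it could cue the answer. That stands. A reader might infer from the wording that the item cannot measure any message effect on purchase; for Sessions 2 and 3 the documents do not support this.

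A reader might also infer that the item asks about an unfamiliar product, that most answers will sit at the bottom of the scale, and that power will collapse. The documents do not support these steps either. Section 11.2 matches the variety to usual menthol use, and neither the criteria in Sections 7.2 and 7.3 nor the screener in Appendix B excludes people who already smoke Marlboro or the study variety. No usual-brand mix, Juster distribution or willingness to switch is given. The corrected error rate of 0.05/6 in Section 22.1 is stated for the packaging comparisons, not for this score, and no power is claimed for it.

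The stakes are also limited. Section 3 lists perceptions of messaging as a secondary endpoint, and Section 22.1 does not name purchase intention. The primary product-evaluation scales bear more directly on appeal. This too stands.

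Finally, moving wholly to a question about the usual brand would change what is asked at Sessions 2 and 3 and give up the link to the product smoked in the field. That is a fair limit on the remedy. None of these replies meets the Session 1 problem.

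**Conclusion.** The point holds for Session 1 without any assumption about data: the plan requires purchase ratings by message, the one printed item cannot give them, and no other item in Appendix C substitutes. All the planned Session 1 purchase ratings are affected (900 to 1,200, depending on whether the no-message pack is rated), and with them the baseline for later change.

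For Sessions 2 and 3 the point is narrower. The randomized comparison is usable as an indirect measure of message effect on intention to buy the study cigarette, but its referent needs stating, above all for the laboratory-made version. How far that version weakens the comparison cannot be sized, because its share is not given.

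This is one component of a secondary endpoint. It leaves the primary endpoints untouched. It deserves correction because the repair is small and a Session 1 rating cannot be recovered once the session has passed.

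**What to change.** **Session 1.** Replace the stem with one that names the pack shown, asked once per message on the same 0–10 scale. For example: 'If your usual cigarettes were sold in a pack carrying this message, how likely are you to buy them in the next month?' For the no-message condition, use 'in their present pack'.

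**Sessions 2 and 3.** Ask the same stem for the assigned message, so that it has a Session 1 baseline. Keep the study-product item alongside it, with the referent spelled out: 'the study cigarettes you have been using, in the pack provided'. Add 'if they were sold' for participants given the laboratory-made version.

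**Documents.** Move the item in Appendix C out of the block for measures given after each cigarette, and state in Section 11.4 which version is used at which session.

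**Cost.** An edit to Appendix C and REDCap, one extra short item at each of Sessions 2 and 3, and some loss of wording match with the sister studies. No visit is added.
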